5.8. Quality research and verification

The quality standard of the original solution and vaccine were formulated according to the 2010 Edition "China Pharmacopoeia" (third) and European Pharmacopoeia. The sample batch of clinical trial (201501002) was commissioned and verified by the National Institute for Food and Drug Control (NIFDC), and the results were in accordance with the quality standards. The self-check results of the vaccine are consistent with the results of NIFDC.

Vaccines quality standard inspection

No.	Verified items	Standard	201501002 (NIFDC)
1	Physical Appearance	White or milky white loose body, after adding the diluents with labeled amount, dissolved as a colorless transparent liquid after shaking , no visible foreign particles.	Conforms with the regulations
2	Titration on 293 cells (IFU/dose)	$\geq 1 \times 10^8$	6.7×10^8
3	The identification of Viral vectors	Amplified fragment size should be consistent with the theory(735bp)by PCR	Conforms with the regulations
4	pH	7.0~8.0	7.4
5	The identification of target gene	Amplified fragment size should be consistent with the theory(2000bp)by PCR	Conforms with the regulations
6	Moisture (%)	≤ 3.0	0.7
7	Detection of EBOV Expression from Infected 293 cells	The antigen expression should be positive by Western blot method	Conforms with the regulations
8	Sterility test	Sterility	Conforms with the regulations
9	Virus particle number (vp/dose)	$\geq 2.0 \times 10^{10}$	4.6×10^{10}
10	Bacterial Endotoxin	≤ 50	<10

	Detection(EU/dose)		
11	Purity (%)	≥ 95.0	98
12	Abnormal Toxicity Detection	Animals should be fully healthy within the observation period, and no abnormal reaction, Each animal weight gain maturity.	Conforms with the regulations
13	Osmolarity (mosm/kg)	400~650 mosm/kg	440

5.9. Package

The vaccine will be packed in a box with labels. The label contains at least the following information: vaccine name, lot number and duration of vaccine, and vaccine preservation conditions and “only for clinical studies”. Sample of label on the vial:

Only for clinical studies
 
Recombinant Human Type 5 Adenovirus Vector
 
Based Ebola Virus Disease Vaccine
 
4×10^{10} vp/vial
 
Lot: 201501002
 
Date: 2015.01.28
 
Exp: 2016.01.28
 
Storage: at 2~8°C, avoid light
 
Beijing Institute of Biotechnology
 
Tianjin CanSino Biotechnology Inc.

Sample of label on the packaging box:

Only for clinical studies
 
Recombinant Human Type 5 Adenovirus Vector
 
Based Ebola Virus Disease Vaccine
 
For one individual
 
Lot: 201501002

Date: 2015.01.28 Exp: 2016.01.28

Storage: light avoided 2~8°C

- Usage and dosage: add 1ml water for injection solution, use immediately after shaking, intra-muscular injection at the lower edge of deltoid muscle in upper arm of 0.5ml.

Contraindications:(1) Allergic to any ingredient of the Ad5-EBOV (2) Acute disease, severe chronic diseases, chronic disease acute exacerbation and fever (3) Seizure, epilepsy, brain or other mental disease(4)Adults over the age of 18, excluding pregnant women.

Adverse reactions:

Notice:

(1) Cracked vials, unclear or failure label, abnormal appearance after rehydration are not allowed to use; (2) Drug as adrenaline should be equipped for use in case of severe allergic reaction. The participants should be observed at least 60 minutes after injection.

Producers: Beijing Institute of Biotechnology/Tianjin CanSino
Biotechnology Inc.

Address: [name] / [name]
[name]

5.10. Transportation and Storage

The vaccine must be stored in a safe, locked place to avoid unauthorized access. The vaccine storage conditions must be assessed in study center to ensure that the vaccine is stored under appropriate conditions in the study. The temperature of vaccine transportation from Beijing Institute of Biotechnology/Tianjin CanSino Biotechnology Inc. to the research center, the remaining vaccine after inoculation back to the research center should be kept at 2-8°C. When the vaccines are received, the quantity, quality and maintenance of the cold chain must be checked, and the "vaccine delivery" form should be filled in.

The temperature of the monitoring instrument, transport and storage of the vaccine should be monitored (Am and PM manually) daily. Once the temperature deviation happens, as the temperature over the provisions of the range of 2-8°C, the investigators and sponsors should be immediately informed, and the “cold chain deviation report form” should be filled in, too. The temperature-deviated vaccine should be identified, placed separately and suspended. Continual usage of vaccines must be under written approval by Beijing Institute of Biotechnology/Tianjin CanSino Biotechnology Inc. Vaccine out of requirements should be on-site sequestration.

6. STUDY OBJECTIVES

To evaluate the safety and immunogenicity of the Adenovirus type 5 vector based Ebola virus disease vaccine (Ad5-EBOV) in healthy adults in Sierra Leone, and determine the appropriate immune dose.

7. STUDY DESIGN

7.1. Design methods

This is a single-center, randomized, blind phase II clinical trial. Blind labeled method is performed to keep whole study randomized and blind. The experimental vaccine groups A, B and placebo are randomly encoded by 2:1:1 ratio.

7.2. Study endpoints

7.2.1. Primary endpoints

7.2.1.1. Safety

- Occurrence of solicited adverse reactions within 7 days after vaccination.

7.2.1.2. Immunogenicity

- ELISA antigen-specific assays for antibody to GP responses on day 0, 14, 28 and 168 (month 6).

7.2.2. Secondary endpoints

7.2.2.1. Safety

- Occurrence of unsolicited adverse reactions within 28 days after vaccination.
- Occurrence of serious adverse reaction during the whole follow-up period (6 months).
- Post-vaccination Rate of infected with HIV.

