9.2.3. Blind maintenance

In the process of the blinding, the staffs responsible for preparing the vaccine are non-blind person, who know distribution of participants because the vaccine group A (high dose group) and vaccine group B (low dose group) need different vaccine preparation methods (see 9.3.2).

Besides the staffs for vaccine preparation, all other researchers do not know the treatment allocation of participants. The two un-blinded staffs only responsible for the vaccine preparation, are not allowed to do any records or tell any person the distribution of participants or participate in the test of any other work (including follow-up observations).

After the visit of 28 days after vaccination, the data will be checked by the statistical part and then locked for the interim analysis. The data will be unblinded. Serious adverse event after day 28 and final visit at month 6 will be opened. But the staffs responsible for the laboratory tests will be kept in blinded during the whole study, including the serum tests at month 6.

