9.4.2. Safety observation and grade of adverse reaction/event

9.4.2.1. Definition of adverse event and serious adverse event

An adverse event (AE) is any untoward medical occurrence in a participant administered an

investigational product and which does not necessarily have a causal relationship with this treatment. A serious adverse event/reaction (SAE) is occurrence of any untoward medical during the whole study period that:

- Results in death.
- Is life-threatening (an event in which the participant is at risk of death at the time of the event; it does not refer to an event which hypothetically might have caused death if it was more severe).
- Results in persistent or significant disability/incapacity.
- Requires hospitalization or prolongation of an existing hospitalization.
- Is a congenital anomaly/birth defect.

In addition, medical and scientific judgment will be exercised in deciding whether other conditions will also be considered serious, such as important medical events that may not be immediately life-threatening or result in death or hospitalization but may jeopardize the participant's safety or may require intervention to prevent one of the other outcomes listed in the definition above. These will also be considered serious. Examples of such events are intensive treatment in an emergency room or at home for allergic bronchospasm; blood dyscrasias or convulsions that do not result in hospitalization; or development of drug dependency or drug abuse.

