9.4.2.2. Grading for adverse events

All adverse events will be graded according to “The standard guidelines for adverse reactions grading of vaccine clinical trials” issued by China state Food and Drug Administration (SFDA). The presence of solicited and unsolicited adverse events and any serious adverse events will be described in terms of the incidence, intensity and relation to vaccination. The incidence of adverse events will be based on the most severe response, and expressed in terms of the number and proportion of individuals who had adverse events in each group.

Injection site

Pain (at the injection site)

Grade 1(mild)= Mild pain when the injection site was touched

Grade 2(moderate)= Moderate pain when the injection site was touched

Grade 3(severe) = Severe pain, refuse to be touched at the injection site

Grade 4(potentially life threatening) = Need emergency treatment or hospitalization

Induration (at the injection site)

Grade 1 (mild) = Diameter : <15mm

Grade 2 (moderate) = Diameter :15~30mm

Grade 3(severe)= diameter >30 mm- ≤ 50 mm

Grade 4 (potentially life threatening)= Gangrene

Redness (at the injection site)

Grade 1 (mild) = Diameter : <15mm

Grade 2 (moderate) = Diameter : 15~30mm

Grade 3(severe)= Diameter : >30mm

Grade 4(potentially life threatening)= Gangrene

Swelling (at the injection site)

Grade 1 (mild) = Diameter : <15mm, with no limited movement

Grade 2 (moderate) = Diameter :15~30mm; with limited movement

Grade 3(severe)= Diameter :>30mm; with severely limited movement

Grade 4(potentially life threatening) = Gangrene

Rash (at the injection site)

Grade 1 (mild) = Diameter : <15mm

Grade 2 (moderate) = Diameter :15~30mm

Grade 3(severe)= Diameter :>30mm

Itch (at the injection site)

Grade 1 (mild) = Mild itch at injection site

Grade 2 (moderate) = Moderate itch on injected arm

Grade 3(severe)= Severe itch all over the body

Systemic reactions

Fever (axillary temperature)

Grade 1(mild) = $\geq 37.1^{\circ}\text{C} \leq 37.5^{\circ}\text{C}$

Grade 2(moderate) = $\geq 37.6^{\circ}\text{C} \leq 39.0^{\circ}\text{C}$

Grade 3(severe) =>39.0°C

Allergic reactions

Grade 1(mild) = Itch without rash

Grade 2(moderate) = Localized urticaria

Grade 3(severe) = Generalized/extensive urticaria, angioedema

Grade 4(potentially life threatening) = Severe allergic reactions

Headache

Grade 1(mild) = Mild, with no interfere with daily activities

Grade 2(moderate) = Moderate, with a mild impact on daily activities

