9.4.4. Relationship between AE and vaccine

Researchers should make the best interpretation of AE, and assess the possible causal relationship between vaccine inoculation and alternative reasons (such as history of underlying diseases, combined treatment of causation). This applies to all AE, including severe and non-severe.

The assessment of causality will be reasonably explained in the following or more aspects of the event:

- The similar reaction to the solution was observed in the past;
- identical events of similar types solution have been reported in the literature;
- the incident occurred along with the time of the vaccination, and again after the secondary vaccination

According to definitions, all the collected AE (that is, the local adverse event of the collection of the report) will be considered to be related to vaccination.

The causal relationship of AE should be evaluated according to the following questions, and according to your judgment, the reasonable possibility of relationship between AE and vaccination is caused by the vaccination:

- Related: there is a suspicion that a link between vaccine and the AE (do not need to be determined); the vaccine has a reasonable potential for promoting the AE.
- Unrelated: there is no suspicion that a link exists between vaccine and the AE; there are other more likely causes, and vaccination has not been suspected to promote the AE.

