9.4.5. Reporting of SAEs

Any serious adverse event, including death due to any cause, which occurs during this study, whether or not related to the investigational products, must be reported immediately. The un-blinding of single cases by investigators in the course of the clinical trial will only be performed if relevant for the safety of the participant.

[figure not shown]
The SAE report form must be filled and submitted to Pharmacy Board of Sierra Leone and the

Sierra Leone Ethics and Scientific Review Committee within 48 hours of the first knowing about the occurrence of the event. All SAEs will be recorded on the case report form and source documents.

In case of death of a participant post-vaccination, and may be correlated with the vaccination, verbal autopsy must be carried out as per WHO Guidelines using “The 2014 WHO verbal autopsy instrument” (Appendix 12, <http://www.who.int/healthinfo/statistics/verbalautopsystandards/en/>). A copy of autopsy report should be attached with the SAE form.

All suspected adverse reactions related to an investigational products, both in unexpected and serious (SUSARs) are expedited reporting to investigator. Also post-study SUSARs that occur after the patient has completed a clinical trial and are reported by an investigator to the sponsor, qualify for expedited reporting.

The sponsor is responsible for the prompt notification to all concerned investigators, the fatal or life-threatening SUSARs will be notified by the sponsor to the Pharmacy Board of Sierra Leone as soon as possible but no later than seven calendar days after the sponsor has first knowledge of the minimum criteria for expedited reporting. All other SUSARs and safety issues deserving expedited reporting must be reported to the competent authority and -dependent on national provisions - to pharmaceutical supervision department in Sierra Leone as soon as possible but no later than 15 calendar days after the sponsor has first knowledge of the minimum criteria for expedited reporting. The SAEs/ SUSARs report procedure should as follows:

Sponsor will also be responsible for reporting the SAEs to the DSMB for safety review. The fatal or

life-threatening SUSARs no later than seven calendar days. Other SUSARs no later than 15 calendar days.

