9.7.5. Statistical methods

9.7.5.1. Safety analysis methods

Safety analysis of this experiment is mainly descriptive analysis of incidence rate of adverse reaction

or adverse events. A chi-square test can be used to compare the proportion of participants with adverse reactions in different groups, Fisher's exact test will be used when it is necessary.

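### The six-month serious-event endpoint does not say whether unrelated events count, and the protocol contradicts itself on who is blind when causality is judged after the day-28 lock

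*Protocol*

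**What the plan says.** All references are to the Protocol.

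- **Endpoint (7.2.2.1, repeated in the Protocol Summary).** The six-month endpoint is "Occurrence of serious adverse reaction during the whole follow-up period (6 months"; the 28-day endpoint is "Occurrence of unsolicited adverse reactions within 28 days after vaccination". Both say reaction, not event.
- **Test (9.7.5.1).** The safety analysis is called mainly descriptive and first mentions adverse reactions or adverse events. The next sentence allows a chi-square or Fisher test to "compare the proportion of participants with adverse reactions in different groups".
- **Definition (9.4.2.1).** "A serious adverse event/reaction (SAE) is occurrence of any untoward medical during the whole study period that" meets one of the listed seriousness criteria. No causal link is required.
- **Causality (9.4.4).** Each event is classed as related or unrelated by judgement. Unrelated means, among other things, that "there is no suspicion that a link exists between vaccine and the AE".
- **Capture and description (9.4.5, 9.4.2.2).** Every serious event, "whether or not related to the investigational products, must be reported immediately", and "any serious adverse events will be described in terms of the incidence, intensity and relation to vaccination".
- **Blinding after day 28.** Section 9.2.3 says the data are unblinded after the day-28 visit and lock, and that "Serious adverse event after day 28 and final visit at month 6 will be opened", with laboratory staff alone kept blind. Section 9.2.2 places unblinding after the last participant's day-28 visit and database lock, with the sponsor, investigator and statistical representatives involved. Section 9.7.2, on the same interim step, says the statistical party must not reveal the code and the sites stay blinded.

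**The concern.** Randomisation protects a comparison of all serious events by arm. It does not protect a comparison of events that have first passed through a subjective causality judgement, unless those judging are blind to arm. If the endpoint means related events only, and those who judge relatedness know the allocation, an event in a known placebo recipient is less likely to be called related than the same event in a vaccinee. The arms could then differ through labelling alone.

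The wording matters even if blinding holds. Two analysts working from 7.2.2.1 and 9.7.5.1 could produce different six-month tables, one of all serious events and one of related events, and each could point to text in support.

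**Working it through.** The plan states no figure on this point, so the check compares texts first and then gives an illustration on assumed rates.

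**1. Does the endpoint carry a causality condition?**
- For: 7.2.2.1 says reaction. Section 9.7.5.1 lists reactions and events as alternatives, then names a test for reactions. Section 9.4.4 supplies the related/unrelated split.
- Against: 9.4.2.1 joins event and reaction in one term without a causality condition. Section 9.4.2.2 describes all serious events, with relation as an attribute. Section 9.4.4 does not say that unrelated events leave the endpoint.
- Result: ambiguous. Neither reading is excluded.

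**2. Is causality judged with allocation open?**
- 9.2.3: yes for serious events after the day-28 lock, laboratory staff excepted. Section 9.2.2 also has the investigator among the parties at unblinding.
- 9.7.2: no, the sites stay blinded. Section 9.2.1 also keeps investigators and staff blinded.
- Result: a contradiction, and no blinded causality assessor is named for the period after the lock.

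**3. How much of the follow-up could be open?**
- Last participant enrolled: (168 - 28)/168 = 140/168 = 83%.
- First participant enrolled, if recruitment takes about one month (a reading of the time-table in section 11, taken as 30 days): (168 - 28 - 30)/168 = 110/168 = 65%.
- Time needed to lock the database would lower both figures.

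**4. Which endpoints are exposed?**
- Six-month serious events: yes, on the related-only reading.
- 28-day unsolicited events: no. Unblinding waits for the last day-28 visit.
- HIV infection: no. It involves no causality judgement.

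**5. Illustration (all rates assumed; the protocol gives neither a serious-event risk nor a labelling probability).** Let f be the open share of follow-up, with events spread evenly over time. Let 20% of events be called related while blind, and q_v and q_p be the proportions called related once open. Then

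apparent ratio = [(1 - f) × 0.20 + f × q_v] / [(1 - f) × 0.20 + f × q_p], with equal true risk in both groups.

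- q_v = 0.30, q_p = 0.10, f = 0.655: (0.069 + 0.1965)/(0.069 + 0.0655) = 0.2655/0.1345 = 1.97.
- Same rates, f = 0.833: (0.0334 + 0.2499)/(0.0334 + 0.0833) = 0.2833/0.1167 = 2.43.
- q_v = 0.40, q_p = 0.05: 3.25 at f = 0.655 and 4.88 at f = 0.833.
- q_v = q_p: 1.0.

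In counts, with an assumed 2% risk over follow-up, all serious events number 375 × 0.02 = 7.5 on vaccine (250 + 125 participants) and 125 × 0.02 = 2.5 on placebo, a ratio of 1.0 per participant. Under 30% versus 10% labelling, the related events number 7.5 × 0.2655 = 1.99 versus 2.5 × 0.1345 = 0.34 at f = 0.655, and 2.12 versus 0.29 at f = 0.833. The all-cause count does not depend on the labelling.

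**The case against.** The strongest case against is that the protocol already treats serious events on an all-cause basis: the definition has no causality condition, every serious event is reported, all are described by incidence and relation, and 9.7.4.1 carries relationship only as an attribute. The test in 9.7.5.1 is permissive, and further detail is deferred to an SAP that is not at hand. This stands as far as it goes. The all-cause data will exist and will probably be tabulated. It does not settle what 7.2.2.1 names as the endpoint or what 9.7.5.1 says is compared.

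A second argument is that assessors are protected, because 9.7.2 keeps the sites blinded, 9.2.2 requires causality to be assessed before a code is broken, and under 9.7.6 the DSMB also determines relationship. The first is one side of a contradiction. The second sits in the text on individual emergency code breaks and cannot cover events that arise after a general unblinding. The DSMB is not stated to be blind when it judges relationship, and it may unblind reported cases.

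Third, small counts would rarely mislead a formal test. Even at an assumed 4% risk with 40% of vaccinee events and no placebo events called related (375 × 0.04 × 0.4 = 6 versus 0), the one-sided Fisher p is about 0.75^6 = 0.18. That is correct. But the analysis is mainly descriptive, so readers will judge by the displayed counts.

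A reader might infer that the endpoint does count only related events, that causality is judged open from each participant's day 29, and that the six-month comparison is therefore biased. The documents do not support this. The related-only reading is one of two, open assessment is contradicted by 9.7.2, opening waits for the last day-28 visit and the lock, and differential labelling is a possibility rather than a finding.

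**Conclusion.** The point holds as an ambiguity combined with a contradiction. The word reaction in 7.2.2.1 and 9.7.5.1 does not match the causality-free definition in 9.4.2.1, and 9.2.3 and 9.7.2 disagree on blinding after the day-28 lock. If the endpoint is read as related events only and 9.2.3 prevails, the six-month comparison is open to assessment bias over roughly 65-83% of follow-up, given about one month of recruitment and a prompt lock.

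The size of any bias cannot be derived from the documents. The apparent ratios of about 2.0 to 4.9 rest wholly on assumed labelling rates, and equal labelling gives 1.0. The illustration covers only an apparent vaccine excess; that labelling could hide one is conceivable but not shown here. Only the six-month serious-event endpoint is exposed to open labelling.

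**What to change.** - In 7.2.2.1 and the Protocol Summary, define the endpoint as all serious adverse events to month 6, by arm, regardless of causality. For consistent wording, define the 28-day endpoint as all unsolicited adverse events.
- In 9.7.5.1, base the between-arm comparison on these counts, with 95% confidence intervals.
- Report related events as a supplementary description, and mark those whose causality was judged after unblinding.
- Reconcile 9.2.2, 9.2.3 and 9.7.2 on who is unblinded after the day-28 lock.

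For serious events the cost is wording only, since 9.4.5 already requires all of them to be reported and recorded. Displayed event rates will be higher because unrelated events are included. The change removes the labelling risk whichever blinding text prevails. It does not remove every effect of open follow-up: under 9.4.1 adverse events are not actively collected from day 8, so reporting itself could still differ by arm if allocation is known.
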